Lack of reliable methods to determine what causes the pain (nonspecific back pain) makes it difficult to set a specific diagnosis. It is therefore of great importance that new methods are developed to improve the ability to the give a correct diagnose. Furthermore, the effect of different treatment on structural changes of the spine, e.g., different types of exercise, may guide how to best advice patients with different pathologies. With magnetic resonance imaging (MRI) an image of the spine can be obtained, but there is still a lack of evidence of its diagnostic benefit and knowledge if it can determine the origin of back pain. In a previous study using advanced MRI technology groups of individuals exposed to different exercise over a 3-month period demonstrated different disc patterns (22). Furthermore, new MRI techniques have demonstrated altered biodynamic properties on group level, when comparing patients with low back pain and control persons (23).

Purpose

The overall aim is to evaluate two different types of digital training interventions (aerobic, core stability) supervised by physiotherapists compared to daily physical activity in terms of clinical and patient-reported outcome (PROM) in patients with low back pain, both for short- and long-term. Furthermore, to evaluate whether new diagnostic MRI methods can identify longitudinal spine tissue changes and to analyse if there is an exercise-related difference (differences between the training groups). In addition, the ability to participate in the different exercise programs and their effect on pain in relation to baseline MRI findings will be evaluated.

Question / Hypothesis

- Do the clinical (muscle strength, conditioning, mobility, function/physical capacity) and PROM differ between patients with low back pain randomized to 3 different exercise interventions (aerobic, core stability, daily physical activity) after 6 and 12 months?

¹ the capacity of the lumbar-pelvic-hip muscle complex to control lower trunk movement and maintain stability of the vertebral column after skeletal perturbation.

² any activities that raise heart rate and make breathing somewhat harder

- Does patients' physical capacity change over time, and is there a difference between groups?
Does the training effect persist 12 months after ending the training intervention (6 months)?

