Patients who meet the inclusion criteria and agree to participate in the study will undergo a thorough clinical low back examination according to standard routine, and assessment of function and physical capacity performed by an experienced physiotherapist.

Before start, the patient will undergo MRI examination (NÄL, Trollhättan, Sweden) and functional imaging methods without contrast agents (such as diffusion tensor imaging (DTI), DIXON³, magnetic resonance spectroscopy (MRS) and T2 mapping⁴) will be obtained.

Sample size calculation regarding the training intervention: based on a p-value 0.05, power 0.85, SD 0.1 and a minimal clinical change in Visual Analog Scale (VAS)/pain 0.11 (Hawker et al-11) gives 23 people/group.

Sample size calculation regarding MRI: is based on the possibility of detecting a 0.5% difference (power size 0.041) regarding the T2 value between the three occasions with significance level 0.05 and power 0.8. Considering possible dropouts, we expect 30 patients in each group, a total of 90 patients.

Intervention

Training intervention

After completing the clinical low back examination, the patient will initially be randomized to either group 1 & 3, then 2 & 3 (see below). As more units will be included over time (Vänersborg/Trollhättan/Uddevalla, Sweden), we expect several training groups on-going at the same time.

Group 1 Aerobic

Group 2 Core stability

Group 3 Daily Physical Activity

Group 1 & 2 will be training according to the following program for 3 months: 45 minutes 3 times/week, 2 times digitally supervised by experienced physiotherapist and one-time un-supervised training. Then 3 months of un-supervised training with regular follow-up meetings with responsible physiotherapist.

Each training session includes warm-up, specific exercises with the ability adjust according to pain and function, and progression, then final relaxation exercises. Estimated number of participants/group (1&2): 10-12, inclusion rate about 35 patients first year, 35 patients 2nd year and 20 patients 3rd year (only preliminary calculation as we depend on the inclusion rate of patients and number of involved health care centre).

Group 3 (~10 patients will run concurrently with group 1or 2) will receive training instruction regarding daily physical activity equivalent to >150 min/week according to WHO recommendations (7) (11) (12) for 6 months. The activity will be recorded in a health app on the patient's mobile.

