The MR images will be assessed according to clinical routine and in addition, when relevant, according to conventional classification systems for specific morphological changes such as Modic Types, Schmorls nodules, High-Intensity Zones. New objective tissue characteristic measures (histogram analysis, shape/texture analysis and regional analysis) in vertebrae/disc/muscle will be extracted by the software we previously have developed and validated based on artificial intelligence (histogram analysis, shape/texture analysis and regional analysis) (30)

Data analysis

All data will be documented in a separate database. This database will be password protected and only those directly involved in the study will have access to the database. In addition, all personal data will be pseudonymised according to EU general data protection rules (GDPR) before exported into SPSS (<https://www.ibm.com/products/spss-statistics>). Data will only be analysed at the group level.

The questionnaires in Webropol will be exported to SPSS for analysis.

Descriptive statistics will be presented as mean/standard deviation or median/range. Comparisons between and within groups will be conducted using either parametric or non-parametric statistical methods depending on data quality. Bonferroni correction will be performed when multiple comparisons are done. All statistical tests will be 2-tailed with statistical significance level of $p < 0.05$.

Spearman rank correlation will be used analysing the association between specific morphological changes and clinical data. In addition, multiparametric prediction modelling will be performed (based on unsupervised/supervised machine-learning).

Expected result / Clinical relevance

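### Single-step Bonferroni is valid, but Holm's step-down rule keeps the same 5% family-wise bound and never rejects less; this is a cheap improvement, not an error

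*Protocol*

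**What the plan says.** The Data analysis section of the protocol gives one multiplicity rule: "Bonferroni correction will be performed when multiple comparisons are done". It adds: "All statistical tests will be 2-tailed with statistical significance level of" 0.05. It allows parametric or non-parametric tests, between and within groups. It does not say which comparisons form a family or how many there are.

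The first question under Question / Hypothesis asks whether outcomes differ between patients "randomized to 3 different exercise interventions (aerobic, core stability, daily physical activity) after 6 and 12 months". Hypothesis 1 is narrower: supervised training, of either or both kinds, against self-directed daily activity.

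The sample size for the training comparison, under Method & Materials, is "based on a p-value 0.05, power 0.85, SD 0.1", with "a minimal clinical change in Visual Analog Scale (VAS)/pain 0.11", which "gives 23 people/group". The recruitment target is larger: "Considering possible dropouts, we expect 30 patients in each group, a total of 90 patients". No dropout rate is given, and the calculation does not mention Bonferroni.

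Under Data collection, the clinical examination and MRI take place on three occasions. The questionnaires, which carry the VAS, are answered on four.

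**The concern.** The protocol itself fixes the correction, so this is a choice that can be judged now and not a detail left to a SAP. Single-step Bonferroni holds every comparison in a family of m to 0.05/m, even after other hypotheses in that family have been rejected. Step-down rules relax the threshold as hypotheses are rejected and keep the same family-wise bound.

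What is at stake is power for the second and later comparisons. Hypothesis 1 allows for benefit in both supervised arms, and showing both is where single-step Bonferroni loses most. The loss is modest at the large standardised effect that the protocol assumes and grows for smaller effects. Such effects are plausible for the many clinical and patient-reported outcomes that were not sized individually.

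**Working it through.** **Inputs.** From Method & Materials: difference 0.11, SD 0.1 (standardised effect d = 0.11/0.1 = 1.1), power 0.85, 23 per group calculated, 30 per group planned. From Data analysis: two-sided 0.05. Assumption, not in the protocol: a family of m = 3 pairwise group comparisons.

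**The protocol's own figure.** n = 2(z₀.₉₇₅ + z₀.₈₅)²/d² = 2(1.960 + 1.036)²/1.21 = 14.8, so 15 per group (16 with the t distribution), not 23. With 0.05/3 = 0.0167 the critical value is 2.394, and n = 2(2.394 + 1.036)²/1.21 = 19.4, so 20 (21 with t). With m = 6 the result is 23 (25 with t). The stated 23 is therefore not reproduced from the printed inputs. That is a separate matter; here 23 is taken as given.

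**Bonferroni power per comparison at 23 per group, m = 3.** d√(n/2) = 1.1 × √11.5 = 3.730, and Φ(3.730 − 2.394) = Φ(1.336) = 0.909. The exact two-sample t test gives 0.888; pooling the SD over three groups gives 0.895.

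**The three rules.** Order the p-values p₁ ≤ p₂ ≤ p₃ and, for the step-down rules, stop at the first failure.

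| Rule | p₁ against | p₂ against | p₃ against |
|---|---|---|---|
| Bonferroni | 0.0167 | 0.0167 | 0.0167 |
| Holm | 0.0167 | 0.025 | 0.05 |
| Shaffer, three means | 0.0167 | 0.05 | 0.05 |

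No threshold falls from one row to the next, so each rule rejects everything that the rule above it rejects.

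**Why Shaffer's version is valid for three means.** If all three means are equal, an error requires p₁ ≤ 0.05/3, which has probability at most 0.05. If they are not all equal, at most one of the three pairwise nulls is true, and it is never tested above 0.05. Exactly two true nulls is impossible, because equality of means is transitive.

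**Simulated power.** Normal data, d = 1.1, both supervised arms better than Group 3, t tests. Values are Bonferroni / Holm / Shaffer. Pooling the SD over two or three groups moves them by about a point.

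| | 23 per group | 30 per group |
|---|---|---|
| Both contrasts shown | 0.83 / 0.87 / 0.91 | 0.93 / 0.95 / 0.97 |
| Each contrast | 0.90 / 0.92 / 0.94 | 0.96 / 0.97 / 0.98 |
| At least one rejection | 0.96 under all three | 0.99 under all three |

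**Smaller effects, 23 per group.**
- d = 0.845, an illustrative effect with 80% unadjusted power and not the protocol's: both contrasts 0.51 / 0.58 / 0.67; each contrast 0.66 / 0.69 / 0.74.
- Graded means 0, 0.055 and 0.11: each half-size contrast 0.28 / 0.37 / 0.44.

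**Error rates at 23 per group.** With all means equal, the family-wise error is about 0.043 under all three rules. With one true null remaining and d = 1.1 for the others, that null is falsely rejected in about 1.7% / 4.2% / 5.0% of trials. All are within the 0.05 bound, up to simulation error.

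**Larger families.** Bonferroni power per comparison at 23 per group (normal / t) is 86.3% / 82.7% for m = 6, 83.1% / 78.6% for m = 9 and 80.7% / 75.5% for m = 12. The protocol does not say which m applies.

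**The case against.** The strongest reply is that nothing is wrong. Bonferroni is valid, stated in advance, free of distributional and dependence assumptions, and usable with both parametric and rank tests, which the protocol keeps open. No other statement in the protocol contradicts it. All of this stands, and it is why the point is an improvement only.

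A reader might infer that the trial is underpowered because of Bonferroni. The documents do not support that for a family of three. At the printed inputs, power per comparison is about 0.90 at 23 per group, above the planned 0.85, and 0.96 at 30. The protocol never sets showing both arms as its power target. The weaker figures at d = 0.845 rest on an effect that it does not state.

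A reader might also infer that stepping down costs nothing. It does cost something. The extra power uses error margin that Bonferroni leaves unspent, and matching simultaneous intervals are harder to construct.

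Three limits on Shaffer's version also stand:
- The family of three is assumed. Hypothesis 1, and randomisation first to Groups 1 and 3 and then to Groups 2 and 3, can be read as two comparisons with Group 3. Shaffer then reduces to Holm.
- The transitivity argument concerns means. If a rank test's null is only that neither group tends to give larger values, equality need not be transitive and the argument fails.
- Four questionnaire occasions give 4 × 3/2 = 6 pairs, to which the thresholds above do not carry over.

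None of these limits touches Holm, which needs no more assumptions than Bonferroni.

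**Conclusion.** The point holds as an optional, inexpensive improvement. Holm dominates the stated rule at the same family-wise bound, for any family and any valid tests. Shaffer's version goes further where the family is exactly three pairwise comparisons of means.

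At the printed inputs and 23 per group, power to show both supervised arms better rises by about 4 points with Holm and 8 to 9 with Shaffer. At 30 per group the gains are about 2 and 4 points. Power per contrast at 23 rises by about 2 and 4 points. The chance of at least one rejection does not change, so the sample size needed to reject at least one null is unaffected.

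These figures rest on a family of three, normal data with equal SDs, and d = 1.1. Gains are larger for smaller effects. Since the protocol does not define the family, the loss in the real analysis cannot be fixed more closely. It would be wrong to report this as a failure of error control.

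**What to change.** Replace the Bonferroni sentence in Data analysis with, for example:

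> Within each outcome and time point, p-values are adjusted for multiplicity by the Holm step-down procedure. Where the family consists of exactly the three pairwise comparisons of group means, or of the three MRI occasion means, by parametric tests, the Shaffer version may be used: the smallest p-value is tested against 0.05/3 and, if rejected, the other two against 0.05.

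Use Holm for the four questionnaire occasions and for all rank tests. Decide for each outcome, before group data are seen, whether Holm or Shaffer applies. Defining the family by outcome and time point is itself a new decision, and the sponsor should adopt it knowingly.

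The cost is one sentence, with no extra patients, visits or data. Unadjusted 95% intervals can be shown beside the adjusted decisions, labelled as unadjusted. The sponsor also accepts a false-positive rate for a remaining true null closer to the 5% limit.

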- Can new diagnostic MRI methods identify characteristic changes over time in back tissue (disc/vertebra/muscle) in patients with low back pain in the full cohort and/or after different types of exercise intervention (aerobic, core stability, daily physical activity) after 6 - 12 months?
- Are MRI-verified changes in the back detected at base line associated the ability to participate in the training interventions as well as associated with positive effect (pain relief, increased endurance and muscle strength, etc.) after participating in any of the training intervention?
- Is there a relationship between clinical changes (pain, activity level and quality of life/function) and longitudinal changes in MRI verified components of the spine tissues depending on what type of exercise intervention (aerobic, core stability, daily physical activity)?

Hypothesis 1: Supervised digital training (aerobic and/or core stability) led by physiotherapist gives better results regarding clinical and PROM compared to self-training (daily physical activity), and the effect persists after ending the intervention (6 months) in patients with low back pain.

Hypothesis 2: new MRI methods can identify exercise-related changes in the lumbar spine in patients with nonspecific low back pain after undergoing supervised physiotherapy digital training (aerobic and/or core stability).

Hypothesis 3: there is a relationship between identified changes in low back tissues and the effect of different types of exercise interventions in patients with low back pain.

Method & Materials

Patients seeking primary health care (primarily Vänersborg/Trollhättan/Uddevalla, Sweden) for lower back pain will be asked to participate. Inclusion criteria: low back pain > 3 months, 18-50 years, have access to computer/tablet/mobile

Exclusion criteria:

- Inadequate Swedish as the language is an obstacle to be able to fully understand written and oral information regarding the project and to follow training instructions
- Other ongoing treatment/exercise for their low back pain
- Age > 50 years
- Patients with radiating leg pain and other neurological symptoms
- Previous back/neck surgery
- Pregnancy
- Diagnosed systematic diseases engaging the spine as rheumatoid arthritis, ankylosing spondylitis
- Factors that prevent an MRI examination, such as claustrophobia, metal implants, etc.

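### Spearman correlation, the only association method the protocol names, cannot test whether the relation between MRI change and clinical change depends on exercise type, and no other named analysis does

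*Protocol*

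**What the plan says.** Three parts of the protocol bear on this.

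- **Question / Hypothesis.** One research question asks whether clinical changes (pain, activity level, quality of life or function) are related to "longitudinal changes in MRI verified components of the spine tissues depending on what type of exercise intervention". Hypothesis 3 is worded differently: "there is a relationship between identified changes in low back tissues and the effect of different types of exercise interventions".
- **Analysis of MRI examination.** Readers will apply classification systems for "specific morphological changes such as Modic Types, Schmorls nodules, High-Intensity Zones". Quantitative tissue measures (histogram, shape/texture and regional analysis) are described separately.
- **Data analysis.** Three kinds of analysis are named. For groups: "Comparisons between and within groups will be conducted using either parametric or non-parametric statistical methods depending on data quality". For association: "Spearman rank correlation will be used analysing the association between specific morphological changes and clinical data". Then: "In addition, multiparametric prediction modelling will be performed (based on unsupervised/supervised machine-learning"). No inputs or target are given for the modelling. Nothing says whether the correlations are pooled or computed within arms, or how arms would be compared.

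**The concern.** Asking whether a relation depends on the type of exercise means asking whether its strength or direction differs between the three arms. That needs a test comparing the relation across arms. A Spearman coefficient is a single bivariate number, with no arm, no baseline value and no interaction.

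If it is computed on all patients together, two things can go wrong. Opposite relations in different arms can cancel, so a real dependence is missed. And if training shifts both the MRI measure and pain, the pooled coefficient reflects those shifts even when no relation exists within any arm. If it is computed arm by arm, three separate p-values do not test whether the arms differ. At stake is the trial's conclusion on whether tissue change and clinical change go together differently under different training.

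**Working it through.** The protocol gives no power, effect size or sample size for the correlation analysis, so there is no stated figure to reproduce. The check has two parts.

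**1. Matching the named analyses to the question**

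- Group comparisons test one variable at a time between or within arms. They do not test the relation between two variables.
- Spearman correlation tests a relation, but without arm.
- Prediction modelling has no stated inputs or target, so nothing shows that arm, or arm by MRI change, enters it.

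The phrase for what Spearman will be applied to is the one used for the Modic, Schmorl and high-intensity-zone readings. If the sentence covers only those, no named association method covers the quantitative longitudinal measures. If it covers all MRI changes, it still lacks arm. On either reading the question has no named test.

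**2. Size of the problem if the coefficient is pooled**

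Inputs from the protocol (Method & Materials, Data analysis): 3 arms; 23 per group before and 30 after the dropout allowance; two-sided 0.05; VAS difference 0.11 with SD 0.1, so 0.11/0.1 = 1.1 SD. Assumed: normal data, the within-arm correlations, and every arm shift on MRI. Rates are from 4,000 simulated trials per setting, without the Bonferroni correction, and are given as n = 23 / n = 30 per arm.

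*(a) Correlation created by arm effects.* The true within-arm correlation is 0, and both training arms are shifted by d SD on both variables. The shift has variance (2/3)(1/3)d² = 2d²/9 across patients, so the pooled correlation is about (2d²/9)/(1 + 2d²/9):

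- d = 0.5: 0.0556/1.0556 = 0.05
- d = 0.8: 0.1422/1.1422 = 0.12
- d = 1.1: 0.2689/1.2689 = 0.21

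The simulated mean Spearman coefficients agree (0.05, 0.12, 0.21).

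| Shift on both variables | Pooled Spearman rejects |
|---|---|
| 0 | 5.0% / 5.3% |
| 0.3 SD | 6.0% / 5.8% |
| 0.5 SD | 7.4% / 7.4% |
| 0.8 SD | 18% / 21% |
| 1.1 SD | 43% / 53% |

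A Spearman test stratified by arm rejects in 4-5% throughout. With the pain shift held at 1.1 SD (10,000 trials), pooled rejection depends on the MRI shift: 6% / 7% at 0.2 SD, 8% / 9% at 0.3 SD, 13% / 16% at 0.5 SD.

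*(b) Dependence on arm, no shift.* The heterogeneity test compares the three Fisher z values, z = arctanh(r), with variance 1.06/(n - 3). This is 1.06/20 = 0.053 for n = 23 and 1.06/27 = 0.039 for n = 30. The statistic Σ(z - mean z)²/variance is compared with 5.991 (chi-square, 2 df).

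| Within-arm correlations | Pooled Spearman rejects | Heterogeneity test rejects |
|---|---|---|
| 0.5, 0, -0.5 | 5% / 5% | 83% / 93% |
| 0.5, 0.5, 0 | 77% / 88% | 37% / 48% |

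In the first row the pooled test stays at its nominal level although the arms differ strongly. In the second it usually finds a relation but says nothing about whether that relation differs by arm. An arm by MRI-change F test in a linear model gives 88% / 96% in the first setting.

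For one pair of arms, 0.5 against 0, power is Φ(arctanh(0.5)/√(2 × variance) - 1.96). For n = 23: Φ(0.549/0.326 - 1.96) = 39%. For n = 30: Φ(0.549/0.280 - 1.96) = 50%.

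**The case against.** A reader might infer that Hypothesis 3 is left unanswered by the analysis assigned to it. The document does not support that. Data analysis assigns Spearman to no hypothesis, and Hypothesis 3 can be read as plain association, which within-arm Spearman could address. The wording about dependence belongs to the research question. The Spearman sentence may instead serve the question on baseline MRI findings, which asks for no arm comparison and where exercise cannot shift the scan.

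A reader might also infer that the correlation will be pooled. The protocol does not say so. Within arms the artefact disappears, and coefficients can be compared by Fisher z. That stands, but the comparison is a separate step the protocol does not name. Without it, and with the same true correlation of 0.4 in every arm, single-arm power is 0.45 / 0.57, and the three arm-wise tests disagree on significance in 1 - 0.45³ - 0.55³ = 0.74 (n = 23) or 1 - 0.57³ - 0.43³ = 0.74 (n = 30) of trials. The protocol does not propose reading them that way, so this is only a risk.

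The highest rates in (a) need an MRI arm effect of 1.1 SD, for which the protocol gives no source. Correlations of 0.5, 0 and -0.5 cancel by construction. Both limits are accepted.

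Model detail is commonly left to an SAP, which is not shown. That covers covariates and random effects. It does not cover a named method that does not match a stated question.

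On ranking classifications: present/absent findings such as high-intensity zones can be rank-correlated validly. Only multi-class Modic type, if coded as a scale, is affected.

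**Conclusion.** The point holds in limited form: the protocol asks whether the MRI-clinical relation depends on exercise type and names no analysis that tests it. This needs no assumption about pooling and no simulation.

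The consequences of pooling are conditional. Missing opposite relations (about 5% rejection, against 83-93% for a heterogeneity test) rests on the chosen correlations. A correlation produced by arm effects alone is negligible to small at shifts of 0.5 SD or less on both variables (about 7% at 0.5 SD) and substantial only near 1 SD (43-53% at 1.1 SD). Hypotheses 1 and 2 expect arm effects on both kinds of variable, but their size on MRI is unknown.

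This should be corrected in the analysis wording. It does not affect the randomised comparison of the arms.

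**What to change.** In Data analysis, state which research question the Spearman correlations serve and that they are computed within arms. For the question on dependence on exercise type, name a linear model of the clinical outcome at follow-up (for example VAS at 6 months) on its baseline value, arm, MRI change and arm by MRI change, with the 2-df interaction as the test. If ranks are preferred, within-arm Spearman coefficients with a Fisher z heterogeneity test would serve.

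Keep Spearman as a within-arm descriptive statistic for continuous, ordinal or binary measures, and enter multi-class Modic type as a categorical factor.

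Report the interaction as exploratory, with arm-specific slopes and confidence intervals. Power for a modest interaction is limited: about 37-48% by the heterogeneity test for correlations of 0.5, 0.5 and 0, and lower once Bonferroni correction is applied. A non-significant interaction should not be read as no dependence. Both variables are measured after randomisation, so the result is an association and does not show that tissue change causes the clinical effect.

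The cost is a change of wording. No new data, visits or patients are needed.
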